**Table 13: Criteria for Clinically Notable Electrocardiogram Abnormalities**

Parameter	High Threshold	Low Threshold
QTcF	> 460 msec	< 295 msec
PR	> 220 msec	< 75 msec
QRS	> 120 msec	< 50 msec
QT	> 500 msec	< 300 msec
RR	> 1330 msec	< 600 msec

QTcF = Fridericia correction.

#### 9.4.2.5. Adverse Events of Special Interest

The principle toxicity of inhibiting both PI3K $\delta$  and JAK pathways is expected to be reversible effects on immune function. Combined inhibition may adversely affect both B-cell and T-cell immune function with resultant increased risk of a variety of infections or other immune-related events. Specific AEs, or groups of AEs, will be followed as part of standard safety monitoring activities. These events (regardless of seriousness) will be reported per the SAE reporting timelines (see [Section 8.3.2](#)).

- ALT  $\geq$  5  $\times$  ULN
- AST  $\geq$  5  $\times$  ULN
- Colitis
- Diarrhea  $\geq$  Grade 2

- Rash  $\geq$  Grade 2
- Intestinal perforation
- Pneumonitis
- *Pneumocystis jirovecii* infection
- CMV infection
- Herpes simplex virus infection
- Varicella zoster virus infection
- Exfoliative dermatitis

#### **9.4.3. Pharmacokinetic Analysis**

The PK parameters of  $C_{max}$ ,  $T_{max}$ ,  $C_{min}$ ,  $AUC_{0-t}$ , and  $Cl/F$  will be calculated from the blood plasma concentrations of INCB050465 and ruxolitinib using standard noncompartmental (model-independent) PK methods. The dose-dependent PK parameters ( $C_{max}$  and  $AUC$ ) for INCB050465 and ruxolitinib will be summarized alone and in combination by mean, median, standard deviation, minimum, and maximum. Pharmacokinetic calculations will be performed, if appropriate, using commercial software such as WinNonlin®. Nominal times will be used in all cases, except when the difference between the actual time and nominal time is greater than 15 minutes for samples collected up to 4 hours after administration and greater than 30 minutes for samples collected more than 4 hours after administration; in these cases, actual time will be used for PK analysis. Refer to [Appendix C](#) for a detailed list and description of the PK parameters. The PK parameters will be summarized by part and dose regimen.

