### **1.5.3. Nonclinical Drug Metabolism and Pharmacokinetics**

The absorption, distribution, metabolism, and excretion of INCB050465 have been studied in rats, dogs, and monkeys. Following intravenous (IV) administration, INCB050465 displayed low systemic clearance, representing 26%, 2%, and 5% of the hepatic blood flow in rats, dogs, and monkeys, respectively. The steady-state volume of distribution was moderate in rats (1.5 L/kg) and monkeys (0.7 L/kg) but low in dogs (0.3 L/kg), indicating species differences in distribution. The terminal elimination half-life values were favorable, ranging from 4.0 hours (rat) to 7.3 hours (monkey). The renal excretion of intact INCB050465 was minimal (< 2% across species). INCB050465 has limited penetration across the rat blood-brain barrier. Following oral administration, INCB050465 was rapidly absorbed, with  $T_{max}$  values of 0.3 hours (rat) to 2.5 hours (monkey). The bioavailability of INCB050465 was complete in dogs (100%), and high in monkeys (79%) and rats (74%). Based on preclinical data, the terminal elimination half-life of INCB050465 in human is projected to be approximately 12 hours, and the oral bioavailability is projected to be 70%.

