### **2.2.2. Secondary Endpoints**

- Change and percentage change in spleen volume from baseline through Week 24 as measured by MRI (or CT scan in applicable subjects).
- Change and percentage change in total symptom score from baseline through Week 12 or Week 24 as measured by the Myelofibrosis Symptom Assessment Form version 3.0 (MFSAF v3.0) symptom diary and by the Myeloproliferative Neoplasms Symptom Assessment Form (MPN-SAF).
- Number of subjects with responses according to the 2013 IWG consensus criteria for treatment response in PMF, PPV-MF, and PET-MF.
- Patient Global Impression of Change score at each visit where the variable is measured.
- Population PK parameters of INCB050465 and ruxolitinib alone and in combination (eg, AUC, Cmax) will be summarized.
- Safety and tolerability of the treatment regimens through assessment of AEs and changes in safety assessments including laboratory parameters.

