**Table 9: Schedule of Laboratory Assessments – Part 1, Part 2, Part 3, and Part 4**

	Screening	Baseline	Day 1	Weeks 1, 3 (Day 8, 22) Part 1 ONLY	End of Weeks 2, 6, 10, 14, 18, 22, then Q4W	End of Weeks 4, 8, 12, 16, 20, 24, then Q12W	EOT or Early Termination Visit	Follow-Up 30-37 Days After Last Dose of INCB050465	Notes		
Window				The window for laboratory visits is ± 3 days							
Local Laboratory Assessments											
Serum chemistries	X	X*	X*	X		X	X	X	*Should be taken as close as possible to Day 1 but may be drawn up to 3 days before first dose. Only 1 sample for baseline/Day 1 is required.		
Hematology	X	X*	X*	X	X	X	X	X	*Should be taken as close as possible to Day 1 but may be drawn up to 3 days before first dose. Only 1 sample for baseline/Day 1 is required.		
Coagulation panel	X					X*	X	X	*Required Weeks 12 and 24 and Q12W.		
Urine pregnancy test		X				X*	X*		All female subjects of childbearing potential. *Pregnancy tests should be repeated if required by local regulations.		
Bone marrow biopsy, aspirate, and analysis	X*					X**			*Predose biopsy/aspirate is not required if biopsy has occurred in previous 2 months as long as biopsy/aspirate and data are available for review by investigator and/or sponsor. **Week 24 and Q24W. Samples of biopsy and unstained slides will be sent to a central vendor.		
Central Laboratory Samples*									*The central laboratory is the sponsor or sponsor's designee.		
Lipid panel (requires overnight fast)	X					X*	X		*Required Weeks 12 and 24 and Q12W.		
Serology - hepatitis and HIV	X								HBV, HCV, HIV		
Serology - CMV	X					X*			* CMV measured at Weeks 4, 8, 12, then Q12 weeks.		
Urinalysis	X					X*		X	*Required Weeks 12 and 24 and Q12W.		
Serum pregnancy	X							X	All female subjects of childbearing potential.		
FSH	X								To document hormonal menopause.		
PK samples			X		X*	X*			*PK sampling will occur on Day 1, Week 2, and Week 4 only. See Table 8 .		

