**Table 11: Schedule of Pharmacokinetic Sampling for Part 1, Part 2, Part 3, and Part 4**

Study Day 1	Week 2	Week 4

Subject arrives having withheld both INCB050465 and ruxolitiniba
 
Predose sample = Time 0 sample
 
Administer ruxolitinib
 
Timed samplesb:
 
 
1 hour postdose
 
2 hour postdosec
 
4 hour postdose
 
 
Administer INCB050465
	
Subject arrives having withheld both INCB050465 and ruxolitiniba
 
Predose sample = Time 0 sample
 
Administer INCB050465
 
Timed samplesb:
 
 
1 hour postdose
 
2 hour postdosec
 
4 hour postdose
 
 
Administer ruxolitinib
	
Subject arrives having withheld both INCB050465 and ruxolitiniba
 
Predose sample = Time 0 sample
 
Administer INCB050465 plus ruxolitinib
 
Timed samplesb:
 
 
1 hour postdose
 
2 hour postdosec
 
4 hour postdose
 

a Subjects are also to arrive at the study visits in the fasted state.

b Window for 1-, 2-, and 4-hour collections is  $\pm$  15 minutes.

c Subjects may eat after the 2-hour timepoint sample has been drawn.

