## **7.10. Other Study Procedures**

### **7.10.1. Distribution of Subject Reminder Cards**

Subjects will be provided with a reminder card at each visit. The subject reminder card will indicate the date and time of the next visit, remind subjects to hold their morning dose of both INCB050465 and ruxolitinib on the day of the visit (all study visits including Week 2, not laboratory-only visits), and remind subjects that overnight fast of at least 12 hours is required for all study visits (including Week 2, not laboratory-only visits). Space will be provided on reminder cards for the Week 2 and Week 4 visit to record the time of the evening dose of ruxolitinib for the day before these visits.

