## APPENDIX C. PHARMACOKINETIC ANALYTICAL PARAMETERS

$C_{ave}$	Average steady-state plasma concentration ( $AUC_{0-12h}/12h$ or $AUC_{0-24h}/24h$ )
$C_{max}$	Maximum observed plasma concentration
$C_{min}$	Minimum observed plasma concentration during the dosing interval
$T_{max}$	Time to maximum plasma concentration
$AUC_{0-t}$	Area under the single-dose plasma concentration-time curve from Hour 0 to the last quantifiable measurable plasma concentration, calculated by the linear trapezoidal rule for increasing concentrations and the log trapezoidal rule for decreasing concentrations
$AUC_{0-\tau}$ (ie, $AUC_{0-12h}$ or $AUC_{0-24h}$ )	Area under the steady-state plasma concentration-time curve over 1 dosing interval (ie, from Hour 0 to 12 for BID administration or from Hour 0 to 24 for QD administration), calculated by the linear trapezoidal rule for increasing concentrations and the log trapezoidal rule for decreasing concentrations
$\lambda_z$	Apparent terminal phase disposition rate constant, where $\lambda_z$ is the magnitude of the slope of the linear regression of the log concentration versus time profile during the terminal phase
$t_{1/2}$	Apparent plasma terminal phase disposition half-life (whenever possible), where $t_{1/2} = (\ln 2) / \lambda_z$
$Cl/F$	Oral dose clearance
$V_z/F$	Apparent oral dose volume of distribution
Fluctuation	Steady-state fluctuation ( $[C_{max} - C_{min}] / C_{ave}$ )

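### Protocol 9.4.3 plans AUC0-t and Cl/F by noncompartmental methods from samples that stop at 4 h; it should name the AUC behind Cl/F and be reconciled with the population PK endpoint

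*Protocol*

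**What the plan says.** Protocol Section 9.4.3 lists Cmax, Tmax, Cmin, AUC0-t and Cl/F for both drugs. These "will be calculated from the blood plasma concentrations of INCB050465 and ruxolitinib using standard noncompartmental (model-independent) PK methods". It then summarises Cmax and AUC for each drug alone and in combination, and refers to Appendix C for definitions.

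Appendix C defines AUC0-t as "Area under the single-dose plasma concentration-time curve from Hour 0 to the last quantifiable measurable plasma concentration". It separately defines a steady-state AUC0-tau over 12 h (BID) or 24 h (QD), which Section 9.4.3 does not name. It gives Cl/F no formula.

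On sampling, the note in Table 9 reads "PK sampling will occur on Day 1, Week 2, and Week 4 only". At each of these visits Table 11 has a predose sample ("Predose sample = Time 0 sample") and three timed samples ("Window for 1-, 2-, and 4-hour collections is" 15 minutes either side). Nothing later is scheduled, although Section 9.4.3 has a timing rule for samples taken beyond 4 h.

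Protocol Section 1.5.3 says that "the terminal elimination half-life of INCB050465 in human is projected to be approximately 12 hours". The documents give no half-life for ruxolitinib.

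The secondary endpoint in Protocol Section 2.2.2 is "Population PK parameters of INCB050465 and ruxolitinib alone and in combination". SAP Section 1 likewise assigns a population PK analysis to the sponsor's pharmacokineticist, in a separate report. SAP Section 10.1 records no change to protocol-defined analyses.

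**The concern.** The parameter list does not fit the sampling schedule. With four samples over 4 h, AUC0-t stops well short of the dosing interval, and it is the only AUC that Section 9.4.3 lists beside Cl/F. An analyst who follows that section literally would report a truncated area as the AUC, and might divide the dose by it to get Cl/F.

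The timed samples span 3 h (1 to 4 h), a quarter of a 12 h half-life, and may include absorption. They cannot support a terminal slope, so extrapolation would not repair the area.

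The secondary PK objective compares each drug alone with the combination. A truncated AUC misstates exposure and also responds less than fully to a change in clearance, which is what that comparison is meant to show. The protocol also points to two methods for the same parameters: population PK in the endpoint and SAP, model-independent PK in Section 9.4.3.

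**Working it through.** The plan states no figure for AUC coverage or Cl/F, so there is none to reproduce.

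**Inputs from the documents**
- Sample times 0, 1, 2 and 4 h (Table 11).
- INCB050465 half-life about 12 h (Section 1.5.3) and interval 24 h.
- Linear-up/log-down trapezoids (Appendix C).
- INCB050465 has been taken daily for 2 or 4 weeks by Weeks 2 and 4, and ruxolitinib at a stable dose for at least 8 weeks. Steady state is therefore reasonable.

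**Assumptions**
- One-compartment oral model, noise-free.
- ka of 1, 2 or 4 per h, and half-life varied from 8 to 16 h.
- For ruxolitinib: interval 12 h and half-life 2 to 6 h.

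**Limiting case, instant absorption, INCB050465**

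AUC0-24/AUC0-4 = (1 − 2^(−24/12)) / (1 − 2^(−4/12)) = 0.75/0.206 = 3.6.

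**One profile in full (half-life 12 h, ka 2 per h)**

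Concentrations are scaled so that the true AUC0-24 is 1: C0 = 0.0198, C1 = 0.0668, C2 = 0.0696, C4 = 0.0629.
- 0-1 h, linear: (0.0198 + 0.0668)/2 = 0.0433
- 1-2 h, linear: (0.0668 + 0.0696)/2 = 0.0682
- 2-4 h, log: 2 × (0.0696 − 0.0629)/ln(0.0696/0.0629) = 0.132
- AUC0-4 = 0.244, so Dose/AUC0-4 is 1/0.244 = 4.1 times the true Cl/F.

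Now set C24 equal to the predose value:
- 4-24 h, log: 20 × (0.0629 − 0.0198)/ln(0.0629/0.0198) = 0.746
- AUC0-24 = 0.244 + 0.746 = 0.990, which is 99% of the truth.

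**All settings, by trapezoid on the planned times**

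| Drug and half-life | Overstatement if Cl/F = Dose/AUC0-4 | Share of AUC0-tau recovered with predose at tau |
|---|---|---|
| INCB050465, 12 h | 4.0 to 4.4 | 98 to 99% |
| INCB050465, 8 to 16 h | 3.4 to 4.8 | 98 to 99% |
| Ruxolitinib, 2 to 6 h (assumed) | 1.5 to 2.4 | 90 to 98% |

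In the 12 h model, the exact 0-4 h area is 23 to 26% of AUC0-24.

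**Interaction**

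Halve clearance and keep volume fixed: the half-life goes from 12 to 24 h and the true AUC0-tau doubles. AUC0-4 on the planned times rises only 1.71-, 1.66- and 1.65-fold for ka of 1, 2 and 4 per h.

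**Cross-check on half-life**

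Protocol Section 1.8.3 models a peak of about 10 × IC90 and about 36 h above IC90 for 20 mg. That implies 36 × ln 2/ln 10 = 10.8 h, in line with the 12 h projection.

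**The case against.** The strongest reply is that no passage computes Cl/F from AUC0-t. The two are only listed together, and Appendix C, to which Section 9.4.3 refers, does define AUC0-tau. This stands, so the 4-fold figure is conditional on one reading of an unstated formula.

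A second reply is that a shared 0-4 h window cancels in the alone-versus-combination ratio. It does when clearance is unchanged. It does not when clearance changes, as the 1.65- to 1.7-fold result shows.

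Three stronger readings are tempting, and the documents support none of them:
- A reader might infer that Cl/F cannot be derived at all. It can, from the planned samples with the predose value at tau, or from the population model. Section 9.4.3 just does not say so.
- A reader might infer that the PK objective loses its main readout. The declared endpoint is population PK, reported separately, and the comparison in Section 9.4.3 summarises Cmax and AUC, not Cl/F. The planned outputs in SAP Appendix A name no noncompartmental PK table.
- A reader might infer that the reminder cards, which provide space "to record the time of the evening dose of ruxolitinib for the day before these visits", cover the wrong visits, because Table 11 makes Day 1 the ruxolitinib-alone profile. But Protocol Section 7.8.2 assays Day 1 for INCB050465 only and Week 2 for ruxolitinib only, and the cards, which cover Weeks 2 and 4, agree with that. The contradiction lies between Table 11 and Section 7.8.2. SAP Section 10.2.3 also records that enrollment has ended, so a card change would come too late.

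**Conclusion.** The point holds as a mismatch between the analysis text and the sampling schedule. AUC0-t here is AUC0-4, about a quarter of the interval AUC for INCB050465. It is unsuitable as the basis for Cl/F, and it understates a change in exposure. The error in Cl/F would be about 4-fold for INCB050465 if Dose/AUC0-t were used. The ruxolitinib range of 1.5- to 2.4-fold rests wholly on an assumed half-life.

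The figures assume a one-compartment model, the stated ka range and a half-life that is itself a preclinical projection. The recovery figures also assume steady state and a predose sample taken one full interval after the previous dose. A sample drawn 2 to 4 h late (an assumed delay) would read 1 − 0.5^(2/12) = 11% to 1 − 0.5^(4/12) = 21% low at a 12 h half-life.

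A secondary objective is affected; the primary spleen-volume analysis is not. The change should be made because it is cheap and the method conflict is otherwise unrecorded.

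**What to change.** In Protocol Section 9.4.3:
- Report the 0-4 h area under the name AUC0-4, with Cmax, Tmax and the predose concentration.
- State the source of Cl/F and of the AUC compared alone versus in combination. Use either AUC0-tau, with the steady-state predose concentration as the value at tau (24 h for INCB050465, 12 h for ruxolitinib), or the population PK model.
- Reconcile the section with the endpoint in Section 2.2.2 and with SAP Section 1. If the protocol will not be amended again, record the choice in SAP Section 10.1.
- Do not report lambda-z, t1/2 or Vz/F from the 1 to 4 h samples. Fluctuation may stay if Cave comes from AUC0-tau.

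Separately, reconcile Table 11 with Section 7.8.2 on which drug is assayed on Day 1 and at Week 2. As written, Table 11 gives ruxolitinib before the Day 1 timed samples and INCB050465 before those at Week 2, while Section 7.8.2 assays the other drug each time.

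The cost is wording only, with no extra samples. The downside is fewer noncompartmental parameters and reliance on a steady-state assumption for the predose value.

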## 9.5. Interim Analysis

### 9.5.1. Interim Safety Analysis

The Part 1 safety run-in portion of the study will test up to 3 doses of INCB50465 in combination with ruxolitinib for a 28-day assessment. During the safety-run in portion of the study, dose escalation between Cohorts 1 and 2 will follow a 3 + 3 design algorithm. Doses will be selected for Part 2 based on the safety outcomes in the Part 1 safety run-in portion of the study according to the rules outlined in [Table 14](#). In the table, a cohort is considered toxic if 2 or more of the first 6 subjects experience a DLT. A cohort is considered safe if fewer than 2 of the first 6 subjects experience a DLT (see [Table 2](#) and Section 4.1.1), with the exception that Cohort 1 will also be considered for escalating to Cohort 2 if 0 of the first 3 subjects experience a DLT. There will be alternative allowance to assess additional doses if Cohort 3 is determined to be above the MTD.

**Table 14: Matrix of Part 2 Dose Selection Based on Part 1 Safety Outcomes by Dose Cohort**

Cohort 1 10 mg QD	Cohort 2 20 mg QD	Cohort 3 5 mg QD	Decision for Part 2
Toxic	Toxic	Safe	Single group or explore dose < 5 mg QD
Safe	Toxic	Safe	Randomized between 5 mg QD and 10 mg QD
Safe	Safe		Randomized between 10 mg and 20 mg QD
Toxic	Toxic	Toxic	Terminate or explore doses < 5 mg

The probabilities of declaring a dose to be tolerable for the 3 cohorts at various DLT rates are provided in [Table 15](#).

**Table 15: Probability of Declaring a Dose to be Tolerable**

True DLT Rate	Probability of Declaring the Dose to be Tolerable	
	In Cohort 1	In Cohorts 2 and 3
20%	70.8%	65.7%
30%	49.4%	42.0%
40%	30.9%	23.3%
50%	17.2%	10.9%
60%	8.02%	4.01%

For example, if the true DLT rate is 50% for a cohort, then there is a 17.2% chance that the dose in Cohort 1 will be considered tolerable and selected for treatment in Part 2 and a 10.9% chance that the dose in Cohorts 2 and 3 would be declared tolerable for treatment in Part 2. Further, if the true DLT rate is 20%, then there is a 70.8% chance that the dose in Cohort 1 would be declared to be tolerable for treatment in Part 2 and a 65.7 % chance that the dose in Cohorts 2 and 3 would be declared tolerable for treatment in Part 2.

### 9.5.2. Interim Efficacy Analysis

There will be 1 planned interim analysis conducted for futility for this study. The interim analysis will be conducted during the randomized portion of the study once TG5D and TG5I/M + TG5 enroll 15 subjects and have been evaluated for spleen volume at Week 12. Further enrollment in a treatment group will be terminated if fewer than 4 subjects in the treatment group have spleen stability or a reduction from baseline in spleen volume (ie, percentage change from baseline  $\leq 0\%$ ) as measured by MRI (or CT scan in applicable subjects) at Week 12. Subjects remaining in any terminated group may have their dose adjusted to reflect the ongoing group with sponsor approval.

If either TG5D or TG5I/M is terminated, then Part 4 will continue as a single-group study, and the primary endpoint will be analyzed as described in Section 9.4.1.4. If both of the treatment groups are terminated, then the study will be terminated. The probabilities of stopping a treatment group for futility for various probabilities of a subject achieving  $\geq 0\%$  decrease in spleen volume at Week 12 are provided in Table 16.

**Table 16: Probability of Stopping a Treatment Group for Futility**

Probability of Subject Having $\geq 0\%$ Decrease in Spleen Volume at Week 12 in a Treatment Group	Probability of Stopping a Treatment Group for Futility
5%	99.5%
10%	94.4%
20%	64.8%
25%	46.1%
30%	29.7%
40%	9.1%
50%	1.8%

## **10. ETHICAL CONSIDERATIONS AND ADMINISTRATIVE PROCEDURES**

### **10.1. Investigator Responsibilities**

This study will be performed in accordance with ethical principles that originate in the Declaration of Helsinki and conducted in adherence to the study Protocol; GCPs as defined in Title 21 of the US CFR Parts 11, 50, 54, 56, and 312; ICH E6 GCP consolidated guidelines; and local regulatory requirements as applicable to the study locations.

The investigator will be responsible for:

- Permitting study-related monitoring, sponsor audits, IRB/IEC review, and regulatory inspections by providing direct access to source data and other relevant clinical study documents.
  - Monitoring: Qualified representatives of the sponsor or its designee, study monitors, will monitor the study according to a predetermined plan. The investigator must allow the study monitors to review any study materials and subject records at each monitoring visit.
  - Auditing: Qualified representatives of the sponsor or its designee may audit the clinical study site and study data to evaluate compliance with the Protocol, applicable local clinical study regulations, and overall study conduct. The investigator must allow the auditors to review original source records and study documentation for all subjects.
  - Regulatory inspection: Regulatory authorities may conduct an inspection of the study and the site at any time during the development of an investigational product. The investigator and staff are expected to cooperate with the inspectors and allow access to all source documents supporting the CRFs and other study-related documents. The investigator must immediately notify the sponsor when contacted by any regulatory authority for the purposes of conducting an inspection.
- Obtaining informed consent and ensuring that the study subjects' questions have been answered and the subjects fully understand study procedures:
  - Informed consent must be obtained before any study-related procedures are conducted, unless otherwise specified by the Protocol.
  - Informed consent must be obtained using the IRB/IEC-approved version in a language that is native and understandable to the subject. A template will be provided by the sponsor or its designee. The sponsor or its designee must review and acknowledge the site-specific changes to the ICF template. The ICF must include a statement that the sponsor or its designee and regulatory authorities have direct access to subject records.

- Obtaining approval from the IRB/IEC before the start of the study and for any changes to the clinical study Protocol, important Protocol deviations, routine updates, and safety information in accordance with institutional requirements and local law.
  - The investigator is responsible for ensuring that the safety reports provided by the sponsor are reviewed and processed in accordance with regulatory requirements and with the policies and procedures established by the IRB/IEC.
- Adhering to the Protocol as described in this document and agreeing that changes to the Protocol procedures, with the exception of medical emergencies, must be discussed and approved, first, by the sponsor or its designee and, second, by the IRB/IEC. Each investigator is responsible for enrolling subjects who have met the specified eligibility criteria.
- Retaining records in accordance with all local, national, and regulatory laws, but for a minimum period of at least 2 years after the last marketing application approval in an ICH region and until there are no pending or contemplated marketing applications in an ICH region, or if not approved, 2 years after the termination of the test article for investigation to ensure the availability of study documentation should it become necessary for the sponsor or a regulatory authority to review.
  - The investigator must not destroy any records associated with the study without receiving approval from the sponsor. The investigator must notify the sponsor or its designee in the event of accidental loss or destruction of any study records. If the investigator leaves the institution where the study was conducted, the sponsor or its designee must be contacted to arrange alternative record storage options.
  - All CRF data entered by the site (including audit trail), as well as computer hardware and software (for accessing the data), will be maintained or made available at the site in compliance with applicable record retention regulations. The sponsor will retain the original CRF data and audit trail.

